7.1.5 Clinical experience of Afinitor in HR+ breast cancer

Several randomised trials evaluated Afinitor in HR+ breast cancer and showed evidence of efficacy of Afinitor in this patient population.

7.1.5.1 Afinitor monotherapy

In a multicentre, randomised phase II study, a daily dose of Afinitor (10mg) was evaluated in patients with mostly HR+ ABC who had received prior endocrine therapy. In this trial, 19 of the 49 patients enrolled were ER+/HER2-; one CR, two PRs, three stable disease for longer than six months, and six stable disease for less than six months were reported in this subgroup. Median PFS in this subset of 19 patients was 3.5 months (95% CI: 1.9–5.5 months, data source: NCI-Canada). An additional PR was reported in a patient with ER+ HER2-unknown tumour [Ellard 2009].

7.1.5.2 Afinitor in combination with endocrine therapy

The combination of Afinitor with endocrine therapy has been assessed in different disease settings.

A neoadjuvant randomised 270 patient phase II study compared the combination of Afinitor and letrozole to letrozole alone. The overall response rate in the Afinitor arm was higher than that with letrozole alone (68% versus 59% (palpation, P=0.062) and 58% versus 47% (ultrasound, P=0.035), respectively. Additionally, there was a greater anti-proliferative response, with a decrease of the Ki67 proliferation index to <1 in 57% of patients in the Afinitor arm and in 30% of patients in the placebo arm (P<0.01). This reduction in Ki67 was observed only two weeks after initiation of trial therapy [Baselga et al 2009].

In the randomised phase III, double-blind, placebo-controlled study (BOLERO-2 Study), Afinitor in combination with exemestane was compared with exemestane alone in 724 postmenopausal women with HR+ ABC who had a recurrence or progression on letrozole or anastrozole. The median duration of the follow up of the patients was 18 months. Median PFS was 7.8 months for Afinitor plus exemestane versus 3.2 months for placebo plus exemestane (HR: 0.45; 95% C; 0.38-0.54; P<0.0001). Centrally assessed PFS analyses showed a median PFS of 11.0 months for the Afinitor plus exemestane arm versus 4.1 months for the placebo plus exemestane arm (HR: 0.38; 95% CI; 0.31-0.48; P<0.0001). Subgroup analyses showed consistent PFS benefit with combination therapy across all patient subsets. By local assessment, three complete responses (CRs, 0.6%) and 58 partial responses (PRs, 12.6%) were reported for the Afinitor plus exemestane arm, versus only four PRs (1.7%) for the placebo plus exemestane arm. The CBR also was increased with Afinitor plus exemestane therapy (51.3%) versus placebo plus exemestane (26.4%) (P<0.0001). These differences in objective response rate and CBR were also supported by a central radiology review [Piccart et al 2012].

In a 111-patient randomised phase II study in postmenopausal women with ER+ ABC previously pretreated with Als, the combination of Afinitor and tamoxifen showed a significant improvement in PFS (8.6 months versus 4.5 months, P=0.0021) and overall survival (median not reached versus 24.4 months, P=0.0137) relative to tamoxifen alone [Bachelot et al 2012]. Although the results of the phase II trial were encouraging, the small sample size limits their relevance to clinical practice.

7.1.5.3 Safety profile of Afinitor

The following adverse events are considered to be class effects of mTOR inhibitors: stomatitis/oral mucositis/ulcers, infections and infestations, rash and similar events, cytopaenia, haemorrhages, non-infectious pnuemonitis, hyperglycaemia/new-onset diabetes mellitus, renal events, and thromboembolism. The more common metabolic AEs reported with mTOR inhibitors result from inhibitory effects on mTOR-regulated lipid and glucose pathways, while infections stem from the immunosuppressive properties of these agents. Virtually all AEs associated with mTOR inhibitors can be managed effectively with dose modification and/or supportive intervention.

The safety profile of Afinitor observed in the BOLERO-2 study was consistent with prior experience in the oncology setting with events of predominantly low grade (grade 1 or 2) reported. An increased risk of NIP, infection, and stomatitis in the Afinitor plus exemestane arm relative to the control arm (exemestane plus placebo) was observed.

The most common AEs suspected to be related to treatment, with an incidence ≥10%, reported in association with Afinitor plus exemestane therapy were consistent with what was previously reported: stomatitis, rash, fatigue, decreased appetite, diarrhoea, dysgeusia, nausea, pneumonitis, weight decreased, anaemia, epistaxis, hyperglycaemia, thrombocytopenia, and pruritus (see Table 7.1).

The most common grade 3-4 AEs suspected to be related to treatment with an incidence of $\geq 2\%$ were: stomatitis, hyperglycaemia, anaemia, pneumonitis, fatigue, elevated alanine and aspartate transaminase concentrations, elevated γ -glutamyltransferase concentrations, dyspnoea, neutropenia, and thrombocytopenia. No new safety concerns emerged from the BOLERO-2 study compared with previous experience with Afinitor monotherapy or combination therapy.

Further details related to Afinitor safety can be found in the everolimus Investigator's Brochure.

	Afinitor plus exemostane	Placebo plus exemestane
Table 7-1	BOLERO-2 Study: Most common Adverse Patients)	Events (> 10 percent of

	Afinit	or p lus e	exemes	tane _		Place	ebo plu	s e xe n	nest ane	
	(n = 482), %			(n = 238), %						
	Grade	•				Grad	le			
Adverse event (preferred term)	All	1	2	3	4	All	1	2	3	4
Stomatitis	59	29	22	8	0	12	9	2	1	0
Rash	39	29	9	1	0	7	5	2	0	0
Fatigue	37	18	14	4	<1	27	16	10	1	0
Diarrhoea	34	26	6	2	<1	19	14	4	1	0
Nausea	31	21	9	<1	<1	29	21	7	1	0
Decreased appetite	31	19	10	2	0	13	8	4	1	0
Weight decreased	28	10	16	2	0	7	3	5	0	0
Cough	26	21	4	1	0	12	8	3	0	0
Dysgeusia	22	18	4	0	0	6	6	0	0	0
Dyspnoea	22	10	6	5	<1	11	8	2	1	<1
Headache	23	17	6	<1	0	15	13	2	0	0
Arthralgia	21	15	5	1	0	17	11	6	<1	0
Peripheral oedema	21	14	6	1	0	6	5	1	<1	0
Anaemia	21	4	10	7	1	5	2	2	<1	<1
Back pain	15	10	5	<1	0	11	6	3	2	0
Epistaxis	17	16	2	0	0	1	1	0	0	0
Vomiting	17	11	6	1	<1	13	9	3	1	0
Pyrexia	16	13	3	<1	0	7	6	1	<1	0
Pneumonitis	16	7	6	3	0	0	0	0	0	0
Constipation	15	11	3	1	0	13	8	5	<1	0
Back pain	15	10	5	<1	0	11	6	3	2	0
Pruritus	14	11	3	<1	0	7	5	2	0	0
Insomnia	14	10	4	<1	0	8	6	3	0	0
Asthenia	14	7	6	2	<1	4	3	1	<1	0
AST increased	14	6	5	3	<1	6	2	2	1	0
Hyperglycaemia	14	4	5	5	<1	2	1	1	<1	0
ALT increased	12	5	4	3	<1	5	1	2	2	0
Dry mouth	11	10	1	0	0	7	7	<1	0	0
Alopecia	11	9	1	0	0	12	12	0	0	0
Nasopharyngitis	10	9	1	0	0	9	7	2	0	0
Pain in extremity	10	6	3	<1	0	12	5	5	2	0
Urinary tract infection	10	3	7	<1	0	2	<1	2	0	0
GGT increase	10	2	2	5	2	9	1	1	5	2
Abbreviations: ALT, alaning glutamyltransferase.	e amino	transfera	ase; A	ST, a	spartate	amino	otransfe	rase;	GGT,	gamma

7.1.6 **Overview of exemestane**

Exemestane is an irreversible steroidal aromatase inhibitor efficacious in treating postmenopausal patients with ABC. It is indicated for adjuvant treatment of postmenopausal women with ER+ early breast cancer who have received two to three years of tamoxifen and are switched to exemestane for completion of five consecutive years of adjuvant hormonal therapy. It is also indicated for the treatment of ABC in postmenopausal women whose disease has progressed following tamoxifen therapy (in the USA) or anti oestrogen therapy (in the EU). Exemestane is initially recognised by the aromatase enzyme as a false substrate and then transformed through a nicotinamide adenine dinucleotide phosphate hydrogen dependent mechanism to an intermediate that binds irreversibly to the enzyme causing inactivation. Exemestane significantly lowers circulating oestrogen concentrations (oestradiol, oestrone and oestrone sulfate) but has no detectable effect on adrenal biosynthesis of corticosteroids or aldosterone [Aromasin prescribing information, Pfizer-Pharmacia, 2005].

The recommended daily dose of exemestane is 25mg taken orally. Exemestane is rapidly absorbed from the gastrointestinal tract and its bioavailability is limited by first-pass metabolism, but is increased when taken with food. Exemestane is widely distributed, extensively bound to plasma proteins and it appears to be more rapidly absorbed in women with breast cancer (T_{max} 1.2 hours) than in healthy women (T_{max} 2.9 hours). The terminal half-life is 18-24 hours and maximal E2 suppression is reached in seven days [Demers 1993, Plourde 1995 and Buzdar 2003]. Exemestane is metabolised by cytochrome P450 isosyme (CYP) 3A4 and aldoketoreductases. It does not inhibit any of the major CYP isoenzymes, including 1A2, 2C9, 2D6, 2E1 or 3A4. Although no formal drug-drug interaction studies have been conducted, significant effects on exemestane clearance by CYP inhibitors appear unlikely [Aromasin prescribing information, Pfizer-Pharmacia, 2005, Hutson 2005, and Buzdar 2003].

The most frequently reported AEs for exemestane are gastrointestinal disturbances, hot flushes, arthralgia, myalgia, sweating, fatigue, and dizziness. Others include headache, insomnia, somnolence, depression, skin rashes, alopecia, asthenia, and peripheral and leg oedema. Thrombocytopaenia and leucopaenia have been reported occasionally. Reductions in bone mineral density can occur with long term use of exemestane. There were 1058 patients treated with exemestane 25mg once daily in the clinical trials program. Exemestane was generally well tolerated, and AEs were usually mild to moderate. Adverse events occurring in greater than 10% of patients include hot flushes (14%), nausea (12%), insomnia, headache, increased sweating, joint and musculoskeletal pain and fatigue [USPI; Aromasin SmPC August 2008 (UK as RMS for EU MRP)]. Androgenic effects were reported in a limited number of patients (4.3%) [Buzdar 2003].

Refer to the package insert of the local supply of exemestane for more details.

7.2 Rationale for the study

The combination of Afinitor (everolimus, RAD001) with exemestane in the BOLERO-2 study [Baselga 2012] was associated with a statistically significant and clinically meaningful increase in the median PFS, versus exemestane alone. Following approval of Afinitor for breast cancer and introduction of this combination for the management of ER+ ABC after progression on a NSAI into UK clinical practice it is desirable to gain information on how Afinitor is being used and the resultant outcomes, especially with regard to specific toxicities.

Novartis	
Non-interventional study protocol	

Confidential

7.2.1 Stomatitis

Stomatitis is a very common adverse event of therapy with Afinitor and exemestane, often occurring soon after starting treatment and frequently regressing during the course of treatment [Porta 2011]. The frequency of all grade stomatitis and related events from the BOLERO-2 study was higher in the Afinitor and exemestane arm (67%) than in the control arm (12%). Grade 3 events occurred in 8% and <1% of patients, respectively but no grade 4 events were observed.

In the Afinitor and exemestane arm, more than one-third of all stomatitis events (grade \geq 2) were reported in the first two weeks (cumulative risk, 14%). The cumulative risks of stomatitis at six and 48 weeks were 26% and 37%, respectively, for Afinitor and exemestane versus 3% for exemestane and placebo (Figure 1 below).

Figure 1: Cumulative risk estimates for initial onset of grade 22 stomatitis [Rugo 2014]

Abbreviations: EVE, everolimus; EXE, exemestane; PBO, placebo.

Among 39 patients with grade \geq 3 stomatitis in the Afinitor plus exemestane arm, 97% experienced resolution to grade \leq 1 following dose interruption/reduction after a median of 3.1 weeks, and 82% had complete resolution after a median of 7.4 weeks. In the control arm, the median time to resolution from grade 3 to grade \leq 1 was 2.6 weeks (time to complete resolution was not assessable; one of two patients had complete resolution).

In the acute phase, various options are available to the physician to provide relief for the patient. The nature and duration of treatment depend on the degree of severity of the stomatitis and the specific criteria used by the individual physician. Since the data are as yet unclear, no definitive treatment recommendation for stomatitis with Afinitor can be provided. However, stomatitis occurring under treatment with mTOR inhibitors has been seen to differ in nature from the stomatitis that develops under certain chemotherapies. For this reason,

this NIS will record the measures used for prophylaxis and, if necessary, treatment of stomatitis and the outcome of these measures. The study will also attempt to identify predisposing risk factors.

7.2.2 Non-infectious pneumonitis

Non-infectious pneumonitis (NIP) is a class effect of rapamycin derivatives. Cases of NIP (including interstitial lung disease) have also been described in patients taking Afinitor. Some of these have been severe and, on rare occasions, a fatal outcome was observed. A diagnosis of NIP should be considered in patients presenting with non-specific respiratory signs and symptoms such as hypoxia, pleural effusion, cough or dyspnoea. and in whom infectious, neoplastic and other non-medicinal causes have been excluded by means of appropriate investigations. Patients should be advised to report promptly any new or worsening respiratory symptoms. Diagnosis is generally suspected in individuals receiving mTOR inhibitors who develop these symptoms or in asymptomatic individuals in whom a routine chest computed tomography (CT) scan reveals a new ground glass or alveolar infiltrate. In a performed and presented analysis of pneumonitis in breast cancer patients treated with Afinitor [Jerusalem 2009], the observed incidence of NIP in four Novartis-Sponsored studies ([C2222], Baselga 2009; Awada 2008; [J2101], Hurvitz 2009; [J2102] Cardoso 2009) totaling 238 patients did not exceed 3%. In the fifth study involving 49 patients (NCIC CTG, Ellard 2009), the incidence was approximately 10-fold higher. In a more recent study [Omarini 2014], the incidence of NIP was higher than expected compared with the data of the BOLERO-2 study (39% versus 12%). However, most of these were asymptomatic. Severe grade 3-4 cases occurred at the same frequency as in the BOLERO-2 study (4% versus 3%, respectively).

Although such marked differences remain poorly explained, the following points deserve consideration:

- Different monitoring methods across the studies have been applied: more extensive chest assessment by CT scans occurred in studies NCIC CTG, J2101, and J2102;
- Sponsor management guidelines for NIP based on CTCAE grade were developed in 2006, therefore fully implemented only in the J2101 and J2102 studies;
- The regular premedication with corticosteroids before the infusion of weekly chemotherapy could in part explain the low incidence observed in studies J2101 and J2102.

Overall, 20% of patients in the Afinitor plus exemestane arm of the BOLERO-2 study had NIP or related events, compared with <1% in the exemestane alone arm. Grade 3 events occurred in 4% of patients and one grade 4 event was reported. The time course for pneumonitis differed from stomatitis, with few early events and no appreciable plateau. Approximately one-quarter of events (grade \geq 2) occurred within the first 12 weeks (cumulative risk, 5%). Cumulative risks of pneumonitis (grade \geq 2) in the Afinitor plus exemestane arm were 10% and 16% at 24 and 48 weeks, respectively (Figure 2). Among patients with grade 3 pneumonitis in the experimental arm, 80% experienced resolution to grade \leq 1, typically following dose interruption/reduction, after a median of 3.8 weeks. Complete resolution of grade \geq 3 pneumonitis was reported in 75% of patients, after a median of 5.4 weeks.

Figure 2: Cumulative risk estimates for initial onset of grade \geq 2 non-infectious pneumonitis [Rugo 2014]

Abbreviations: EVE, everolimus; EXE, exemestane; PBO, placebo.

8 Research question and objectives

This NIS will prospectively collect UK specific data on the use of Afinitor in combination with exemestane. United Kingdom audit data [Omarini 2014, Thanopoulou 2014] and anecdotal evidence to date has suggested a higher AE incidence than expected from the reported safety profile in the BOLERO-2 study. Of particular interest are two AEs, stomatitis and NIP, both of which are class effects of rapamycin derivatives. Understanding the time course of these AEs will allow appropriate patient education, inform frequency of monitoring and aid in development of prevention and management strategies. The study will also attempt to identify any predisposing risk factors for the development of these two AEs.

8.1 **Primary objective:**

The primary objective of this observational study is to describe, in patients commencing treatment with Afinitor in combination with exemestane for ABC after progression on a NSAI two specific toxicities, namely stomatitis* and NIP* in terms of:

- incidence, severity, length of time to onset, duration and clinical course,
- specific management (prophylaxis and intervention).

The study will also collect data on any possible potential predisposing factors and will include collection of data on past incidence.

*Definition of CTCAE (Common Terminology Criteria for Adverse Events): Non-infectious pneumonitis (NIP) and stomatitis (V4.0 2009)

	Grade 1	Grade 2	Grade 3	Grade 4
Non-infectious pneumonitis (NIP)	Asymptomatic, X-ray images only; no management required	Symptomatic; medical management; daily activities restricted	Severe symptoms; limited personal activities. Oxygen therapy indicated	Life-threatening. Emergency intervention indicated (tracheotomy or intubation)
Stomatitis	Asymptomatic or mild symptoms: no management required	Moderate pain; no interference during oral administration; diet adapted accordingly	Severe pain during oral administration	Life-threatening. Emergency intervention indicated

8.2 Secondary objectives:

- to determine the dosing, schedule and duration of treatment with Afinitor and exemestane including any dose modifications/durations and reason(s); frequency of monitoring; prior and subsequent treatments and reason(s) for discontinuation
- to evaluate investigator-assessed progression-free survival with Afinitor plus exemestane. Investigator-assessed disease progression may be based on clinical examination or radiographic or laboratory features, mirroring routine practice.
- to capture changes in Quality of Life (QoL) scores over time and investigate the relationship between Health-Related Quality of Life (HRQoL), as measured by the EuroQol five-dimensional questionnaire (EQ-5D) and subjective well-being scores in ABC;
- documentation of adverse events (AEs).

9 **Research methods**

9.1 Study design

This is an open-label, NIS of oral Afinitor (everolimus [RAD001]) in combination with exemestane in patients with metastatic or locally advanced ER+ breast cancer after progression on therapy with a NSAI. Afinitor (10mg daily) in combination with exemestane (25mg daily) will be prescribed in accordance with the SmPCs and supplied by pharmacy.

This is a NIS and, therefore, does not impose a therapy protocol, diagnostic/therapeutic procedure, or a visit schedule. Patients will be treated according to local prescribing information and routine medical practice in terms of visit frequency and types of assessments performed and only these data will be collected as part of the study.

The planned observation period per patient starts with initiation of treatment with Afinitor in combination with exemestane, but ends on completion of the observation phase. The observation phase completes once the last patient has been on study for 12 months. All antineoplastic therapies (surgery, medication, radiotherapy) for advanced breast cancer both

prior to initiation of Afinitor plus exemestane and post discontinuation should be recorded on the relevant eCRF pages. The treating physician will be asked to complete, if possible, at every patient visit the appropriate electronic case report form (eCRF). Below is the recommended assessment schedule that most likely mirrors the patterns of routine clinical care of most patients being treated with Afinitor (everolimus) in breast cancer. More frequent visits may be considered appropriate by the treating physician. Under these circumstances an appropriate eCRF should be completed for each visit. Data will be entered into an electronic data capture system allowing for continuous access to data and any potential reevaluations of the study design or conduct.

Time of data entry	At start of documentation	After approx. 2 weeks	Approx. Month 1	Approx. Months 3, and at 3- month intervals thereafter	At end of treatment
Obtain patient's written	х				
Informed consent*	N N				
Inclusion/exclusion criteria	X				
Demography	A Y				
Physical examination	X				
Vital signs	X				
ER, PoR status and Ki67	X				
Relevant medical history/current medical conditions	X				
Concomitant medications	Х				
Date of initial diagnosis	Х				
Date of metastatic relapse (if applicable) and sites involved	x				
Prior antineoplastic therapies (surgery, medication, radiotherapy) for advanced breast cancer	Х				
Prior history of stomatitis	Х				
Metastatic sites involved at initiation of Afinitor and exemestane	х				
Prescription of Afinitor and exemestane	Х		Х	Х	Х
Current tumour treatment with Afinitor (dosage, dose reduction, pauses in treatment, reason for dose adjustment)		х	х	Х	Х
PFS				Х	Х
Patient Quality of Life questionnaires	X	X	X	X	X

Standard well-being questionnaire	Х	Х	х	Х	Х
Planned prophylactic measures and stomatitis treatment	Х	Х	Х	Х	
AEs/SAEs (including stomatitis and NIP)		Х	Х	Х	х
Reason for discontinuing treatment including sites of progression					х
Antineoplastic therapies since discontinuation of Afinitor plus exemestane					х

* Please note that this study allows up to 4 weeks to consent a patient on to the study.

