9.3.4.7 Study discontinuation

At a minimum, all patients who discontinue the study, whether withdrawn prematurely or otherwise and including those who refuse to return for a final visit, will be contacted for safety evaluations 30 days following end of treatment.

If a study withdrawal occurs, or if the patient fails to return for visits, the Investigator must determine the primary reason for a patient's premature withdrawal from the study and record this information on the End of Treatment eCRF page.

At this stage, the following information will be recorded:

- Date and reason for the end of the study (end of the study, treatment withdrawal, discontinuation of follow-up/lost to follow-up, or any other reason);
- Clinical details including best response during treatment;
- Safety data.

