9.3.4.8 Criteria for premature withdrawal

The planned observation period per patient starts with initiation of treatment with Afinitor in combination with exemestane, but ends on completion of the observation phase. The observation phase completes once the last patient has been on study for 12 months. All

antineoplastic therapies (surgery, medication, radiotherapy) for advanced breast cancer both prior to initiation of Afinitor plus exemestane and post discontinuation should be recorded on the relevant eCRF pages.

Patients should be followed until the end of the study except if the following conditions for early termination are met:

- Voluntary discontinuation (withdrawal of patients' consent to collect or use their data);
- Patient lost to follow-up.

All data generated up to withdrawal of consent and the reason(s) for discontinuation will be recorded. Patients who withdraw consent will not be contacted for follow-up information.

Patients who discontinue the study for any reason other than consent withdrawal should be asked to return for an early discontinuation assessment. The reason for discontinuation should be established. All available safety data will be collected for a period of one month following the last dose treatment.

For patients who are lost to follow-up (those whose status is unclear because they fail to appear for study visits without stating an intention to withdraw), the physician should contact the patient and ask them to return for a final assessment. Every effort should be made to obtain a reason for discontinuation. The physician should document steps taken to contact the patient, e.g., dates of telephone calls and registered letters.

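### Table 9-1 and section 9.3.4.7 can be read as ending data collection at treatment stop, while sections 9.1 and 9.3.4.8 follow patients to study end; progression dates and later therapies are at risk

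*Protocol*

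**What the plan says.** Two sets of statements in the protocol bear on how long data are collected.

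**Follow-up continues after treatment.**
- Section 9.1: "The observation phase completes once the last patient has been on study for 12 months". Section 9.3.4.8 repeats this and adds "Patients should be followed until the end of the study except if the following conditions for early termination are met". The only two conditions are withdrawal of consent and loss to follow-up.
- Sections 9.1 and 9.3.4.8 say that antineoplastic therapies "prior to initiation of Afinitor plus exemestane and post discontinuation should be recorded on the relevant eCRF pages".
- Section 9.3.4.2 calls for details of subsequent treatments. Section 9.2.2 has clinical studies entered on progression captured up to study end.
- Section 8.2 makes "prior and subsequent treatments and reason(s) for discontinuation" part of a secondary objective, and makes investigator-assessed PFS another.

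**Collection appears to end with treatment.**
- The last column of Table 9-1 is "At end of treatment". No column follows it.
- The row "Antineoplastic therapies since discontinuation of Afinitor plus exemestane" is marked in that column only.
- PFS is marked there and in the column "Approx. Months 3, and at 3- month intervals thereafter".
- Section 9.3.4.7 gives the reasons for the end of the study as "end of the study, treatment withdrawal, discontinuation of follow-up/lost to follow-up, or any other reason", and has premature study withdrawal recorded on the End of Treatment eCRF page.

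**The concern.** Section 9.3.4.7 treats stopping the drug as a way of leaving the study; section 9.3.4.8 does not. The schedule, which is what a site works from day to day, fits the first reading better. A site that follows Table 9-1 and 9.3.4.7 as written could close a patient at treatment stop and believe it had complied.

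Two secondary objectives would suffer. Subsequent treatments would be asked for at the one visit where few can have begun. For patients who stop because of toxicity before they progress, the progression date would not be obtained. Such stops are foreseen: Table 9-2 includes discontinuation for stomatitis and for pneumonitis. An analysis plan can choose a censoring rule, but it cannot recover dates that no one entered. That is why the point belongs to the protocol.

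**Working it through.** **1. The passages side by side**

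| Question | Table 9-1 and 9.3.4.7 | Other sections |
|---|---|---|
| When does a patient leave the study? | Treatment withdrawal is a listed reason | Only consent withdrawal or loss to follow-up (9.3.4.8) |
| Where is leaving recorded? | End of Treatment page | Not stated separately |
| When are later therapies collected? | One mark, at end of treatment | Required, but with no time point (9.1, 9.3.4.2, 9.3.4.8); further clinical studies on progression, to study end (9.2.2) |
| When is progression collected? | 3-monthly column and end of treatment | General rule to follow to study end; an eCRF at each visit if possible (9.1) |

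The first row is a direct contradiction. In the third, the requirement exists but the schedule does not serve it. In the fourth, nothing expressly covers a patient who stops for toxicity without having progressed. Section 9.2.2 does not help, because it begins at progression.

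**2. How much observation time follows treatment**

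Every patient not lost or withdrawn has at least 12 months of planned observation. The median PFS quoted from BOLERO-2 (section 7.1.5.2, local assessment) is 7.8 months. If PFS is exponential with that median, the share event-free at 12 months is 0.5^(12/7.8) = 0.5^1.538 = 0.34. About 66% would have progressed or died by then. If patients stop at progression, a large part of the cohort has off-treatment time inside the study, and this is where subsequent treatments occur.

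**3. Size of the PFS effect**

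The protocol states no figure on this point to reproduce; section 9.5 sizes the study on incidence of the two toxicities, not on PFS. The following is an illustration.

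Inputs:
- n = 200 (section 9.5) and median PFS 7.8 months (section 7.1.5.2).
- Assumed: exponential times; a share s = 10%, 20% or 30% stopping for toxicity before progression; a hazard after the stop of h = 1.5 or 2.2 times the hazard before it. The value 2.2 is 1/0.45, the quoted BOLERO-2 hazard ratio inverted.

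Formulas:
- Progression hazard λ = ln 2 / 7.8 = 0.0889 per month.
- Toxicity-stop hazard μ = λs/(1 − s) = 0.0099, 0.0222, 0.0381.
- PFS with full follow-up: S(t) = e^(−(λ+μ)t) + μ[e^(−hλt) − e^(−(λ+μ)t)] / (λ + μ − hλ). The median solves S(t) = 0.5.
- If patients are censored at the stop, Kaplan-Meier estimates e^(−λt), with median 7.8 throughout.

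One case in full, s = 20% and h = 1.5: λ + μ = 0.1111, hλ = 0.1333, and μ/(λ + μ − hλ) = −1. At t = 7.53, S = 0.4333 − (0.3665 − 0.4333) = 0.500.

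| s | Stops of 200 | Median, h = 1.5 | Overstated by | Median, h = 2.2 | Overstated by |
|---|---|---|---|---|---|
| 10% | 20 | 7.67 | 0.13 | 7.54 | 0.26 |
| 20% | 40 | 7.53 | 0.27 | 7.26 | 0.54 |
| 30% | 60 | 7.37 | 0.43 | 6.96 | 0.84 |

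A simulation of 400,000 patients on the same assumptions gives 7.64 to 6.94 over the same grid, within 0.03 months of these values. With h = 1 the full-follow-up median is 7.8 and there is no bias, only lost outcomes.

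The direction also depends on the rule. If the stop were counted as an event, the median would be ln 2/(λ + μ) = 7.8(1 − s) = 7.0, 6.2 or 5.5 months, too low rather than too high.

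**The case against.** The best defence is that the protocol's intention is plain and repeated. Later therapies must be recorded under 9.1, 9.3.4.2 and 9.3.4.8, and further clinical studies on progression under 9.2.2. Table 9-1 is a recommended schedule in a study that imposes none; the trigger is the routine visit, and cancer patients still attend after a drug is stopped. The 3-monthly column is not expressly limited to time on treatment, and sections 9.3.4 and 9.4 count those intervals from treatment start without an end.

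Much of this stands, and it rules out three stronger conclusions that a reader might draw:
- **Later therapies have no collection point.** Not supported: four sections ask for them or for part of them. What is missing is a usable time point in the schedule.
- **Resolution of stomatitis or pneumonitis after a stop is lost, so the primary objective is damaged.** Not supported: section 11 has each adverse event followed until it resolves or is judged permanent, whatever the treatment status.
- **PFS will be biased upward.** Not supported as a flat statement. It needs sites to stop following patients, censoring at the stop, and a higher hazard afterwards. The protocol fixes no censoring rule and may leave that to the analysis plan. The factor 2.2 comes from a randomised comparison between arms and need not apply to patients who stop for toxicity.

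The defence does not remove the contradiction over treatment withdrawal. Nor does it settle the 3-monthly column: that column also carries the current Afinitor dosing row, stands before the end-of-treatment column, and belongs to a schedule that section 9.1 presents as mirroring the care of patients on Afinitor. Reading it as on-treatment only is natural, though not certain.

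**Conclusion.** The concern holds as an internal contradiction with a practical consequence. Table 9-1 and 9.3.4.7 can be read as closing data collection at treatment stop; 9.1 and 9.3.4.8 forbid that. Subsequent therapies are required but badly scheduled, and progression after a toxicity stop is covered only by general wording.

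The size is modest and conditional. If 10% to 30% stop for toxicity before progression, 20 to 60 of 200 progression times are at risk. The resulting overstatement of median PFS lies between 0.1 and 0.9 months, given censoring at the stop, a later hazard 1.5 to 2.2 times higher, and no follow-up after the stop. It is zero if the hazard does not change. The stop rate and the later hazard are assumptions; the protocol gives neither. The primary objective is not affected. The point is worth correcting because the lost dates could not be recovered at analysis.

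**What to change.** 1. Reconcile 9.3.4.7 with 9.3.4.8. Separate end of treatment from end of study, in the text and on the eCRF page, and list treatment withdrawal only as a reason for end of treatment.
2. Add a post-treatment column to Table 9-1, completed from routine notes or contact about every 3 months to study end. Mark it for progression or death with dates, and for subsequent antineoplastic therapy with dates. Move or extend the mark for therapies since discontinuation accordingly.
3. State whether the existing 3-monthly column applies only while the patient is on treatment.

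No extra visits are needed and the study stays non-interventional. The cost is an eCRF page and a modest amount of site data entry. How PFS is then censored can be left to the analysis plan.
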